7.6 Screening Failures

All patients signing consent who do not meet the inclusion and exclusion criteria or who do not have the ablation procedure initiated, will be recorded as screen failures. The relevant eCRF pages (demographics, reason for screen failure) will be completed for all screen failure patients and thereby the data will be included in the study database.

7.7 Removal of Patients from the Study

In accordance with the current revision of the Declaration of Helsinki and the Code of Federal Regulations, a patient has the right to withdraw from the study at any time for any reason without prejudice to his/her future medical care by the physician or the institution. Should a patient (or patient's legally authorized guardian/representative) decide to withdraw from the study, all efforts will be made to collect all AEs they may have experienced. Patients who withdraw or are terminated prior to the ablation procedure will be replaced.

Participation may be terminated prior to completing the study for any of the reasons listed below (reasons that do not fit the categories below will be documented as "other").

Withdrawal of Consent:

If a patient chooses to withdraw early from the study, the eCRF completion page should be completed. When a patient's participation is terminated prior to completing the study, the reason for withdrawal is to be documented on the eCRF and in the source documentation.

Ablation:

The Investigator may withdraw a patient during the ablation procedure for any reason, including the following reasons:

1. Inability of Investigator to locate and target the soft tissue lesion.
2. Inability of patient to tolerate the anesthesia.

Death:

When available, the cause of death should be documented.

Lost to follow-up:

All patients should be encouraged to return for protocol required clinic visits for evaluation during the study follow-up period. If a patient is unable to return for a clinic visit or unable to be contacted by telephone, attempts to contact the patient should be documented in the source documents. Only after failing to contact the patient at the final follow-up visit, the patient will be considered lost to follow-up and the primary reason for early termination will be completed in the eCRF.

Site Termination or Study Termination:

The Sponsor may terminate a site or study at any time. When this occurs, all patients at the site will be withdrawn and documented as "early termination." Reasons for site or study termination may include, but are not limited to, the following:

- Administrative concerns (e.g., inadequate patient enrollment, investigator/institution non-compliance, change of business strategy, etc.).
- Safety issues, including those due to non-compliance, which substantially affect the risk-to-benefit ratio of the study patients at a site or for the study as a whole.
- Futility: It is evident that the endpoint cannot be reached given the study design and number of enrolled participants.
- Regulatory body mandate(s).

The Investigator has the right to terminate participation in the study at any time (e.g., for safety or inability to enroll patients). Should termination of a site be necessary, the Sponsor will provide procedures for termination.

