12.2 Reporting Adverse Events

The Investigator is required to report all AEs experienced by the patient from the start of the ablation procedure (Visit 2A) until the patient completes Visit 5 (1 year after the first ablation procedure) or withdraws early (prior to Visit 5) to the Sponsor within 14 days of become aware of the AEs. All AEs (both serious and non-serious) must be reported in the AE eCRF. The Investigator will evaluate the severity of the event and its relatedness to the study device or procedure.

Any necessary medical management of the event will be recorded in the patient's medical record/source document. All AEs must be followed until resolution or until they become stable.

The Investigator will record all AEs (both serious and non-serious) in the source documents. CTC (Common Terminology Criteria) should be used when recording AEs. In addition, the following information should be recorded:

- Onset date
- Resolution date or date of death
- Severity of the event using CTCAE
- Action taken
- Event status (ongoing at study end or resolved)
- Relationship of AE to the ablation device used in the study
- Relationship of AE to the study procedure
- Indication of seriousness.

Data related to SAEs will be collected until event resolution, or until the event is considered stable, or until all attempts to determine the resolution of the event are exhausted. All AEs that are unresolved at study completion (or early termination) will be recorded as ongoing at study end.

Reporting Serious and Non-Serious Adverse Events to the Sponsor

The study site must report all SAEs, whether they are related to the device or procedure, to the Sponsor as soon as possible, but no later 72 hours of becoming aware of the SAE. The study site will report the SAE by entering the event into the EDC system via the Adverse Event eCRF, which will trigger an automated email to the Sponsor. Additional information, including the Investigator's assessment, may be added to the eCRF later; however, the study site must complete the AE eCRF within 72 hours of becoming aware of the SAE. If the Sponsor requires supporting documentation or other information, the Sponsor will contact the study site.

In the event of death, the Investigator must report all available information to the Sponsor.

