The original study protocol planned to continue study enrollment until 40 subjects were ablated (approximately 20 subjects ablated by interventional pulmonologists and 20 subjects ablated by thoracic surgeons) and completed Visit 3 (30 days \pm 7 days after the first ablation procedure). However, study enrollment was temporarily halted after 10 subjects were enrolled to convene a meeting of the Data Safety Monitoring Board (DSMB) following the death of one subject. While the DSMB recommended that the study could continue enrollment, the decision was made to permanently stop study enrollment and follow the 10 previously-enrolled subjects through the end of the study follow-up period of 1 year post-ablation. As such, this decision impacts several of the analyses originally planned in the study protocol and those changes will be identified in the appropriate sections throughout this SAP.

1 Study Overview

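### A stop during ablation or a site closure is written as leaving the study, so AEs and readmissions that begin after investigator or sponsor withdrawal need not be collected

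*Protocol*

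**What the plan says.** Protocol 7.7 opens its list with "Participation may be terminated prior to completing the study for any of the reasons listed below". Two entries matter here.

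- **Ablation.** "The Investigator may withdraw a patient during the ablation procedure for any reason, including the following reasons". The two examples are "Inability of Investigator to locate and target the soft tissue lesion" and anesthesia that the patient cannot tolerate.
- **Site or study termination by the sponsor.** "When this occurs, all patients at the site will be withdrawn and documented as" early terminations. The possible grounds include administrative and business ones.

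Protocol 12.2 has AE reporting run from the start of the procedure "until the patient completes Visit 5 (1 year after the first ablation procedure) or withdraws early (prior to Visit 5". Protocol 6.2 closes the longer safety window at one year or at early discontinuation. Section 12.2 also requires AEs to be followed until they resolve or stabilise, with a matching rule for SAE data.

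The safeguard in 7.7, "all efforts will be made to collect all AEs they may have experienced", belongs to a sentence about a patient, guardian or representative who decides to withdraw.

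On the denominator, Protocol 10.7 and SAP sections 6 and 9.9 require that ablation was received through the flexible probe. The programming note under SAP Table 1 admits any subject with a recorded ablation date.

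**The concern.** Ablation here is a one-time procedure, so stopping it gives no reason to stop observing the patient. Section 7.7 does not keep the two apart: the entry on stopping during ablation sits in a list of ways to leave the study, and leaving the study ends the reporting of new AEs. A complication that starts after the withdrawal, or a readmission that would be recorded at Visit 3, then has no visible route into the data.

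The loss may be related to outcome. An investigator who ends a patient's participation during the procedure does so because something did not go as planned. Whether such patients carry a higher risk of late complications is not stated anywhere, but it cannot be ruled out. Safety is the first secondary objective, and Protocol section 11 acknowledges that the technique may carry unknown risks.

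The analysis cannot repair the loss. AEs are crude subject percentages with no time at risk, SAP 9.9 rules out imputation, and SAP 9.10 rules out sensitivity analyses.

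**Working it through.** The plan gives no figure to reproduce. The target of 40 has no event rate, precision target or dropout rate behind it. The check is first textual, then illustrative.

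**Step 1: who is covered after leaving early**

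| How participation ends | New AEs afterwards | AEs already present |
|---|---|---|
| Patient decides to leave | 7.7 asks for all efforts at collection | Followed until resolved or stable (12.2) |
| Investigator withdraws during ablation | No visible requirement | Same |
| Sponsor closes site or study | No visible requirement | Same |
| Contact lost | Not declared lost until contact fails at the final visit (7.7) | Same |

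The obligation to collect is weakest where the investigator or the sponsor, not the patient, ends participation.

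**Step 2: which denominator the patient falls in**

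- *Some ablation delivered before the stop.* The patient meets the FAS wording and counts in SAP Tables 14 to 21 with truncated observation.
- *No ablation delivered, but an ablation date entered.* The patient is outside the FAS wording of Protocol 10.7 and SAP 9.9, but inside the FAS as programmed.
- *No ablation delivered and no date.* The patient is outside the FAS. Any AEs appear only in Listing 29. Because the procedure was initiated, the patient is not a screen failure for that reason under Protocol 7.6, yet is not clearly treated, and so enrolled, under 7.2.

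Both named stop reasons can arise before any energy is delivered, so the second and third cases are realistic.

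**Step 3: size when such patients stay in the FAS (assumed inputs)**

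Let N be the FAS size, k the number withdrawn on Day 0, p each patient's probability of at least one AE in the window (taken as equal for all), and f the share of that risk falling before withdrawal. The expected number of patients with an observed AE is (N − k)p + kfp. Dividing by Np gives

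observed / true = 1 − (k/N)(1 − f).

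| k | N = 10, f = 0 | N = 10, f = 0.5 | N = 40, f = 0 |
|---|---|---|---|
| 1 | 1 − 0.1 = 90% | 95% | 1 − 0.025 = 97.5% |
| 2 | 80% | 90% | 95% |
| 3 | 70% | 85% | 92.5% |

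With N = 10 and f = 0, a true 20% would appear on average as 18%, 16% or 14% for k = 1, 2 or 3. If withdrawn patients were at higher risk than the rest, the shortfall would be larger.

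**Step 4: what one or two patients do to the reported interval (exact 95% limits)**

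- One unseen SAE subject: 1/10 = 10% (0.3 to 44.5%) against 2/10 = 20% (2.5 to 55.6%).
- Two aborted patients kept in or left out, with 2 events among the others: 2/10 = 20.0% (2.5 to 55.6%) against 2/8 = 25.0% (3.2 to 65.1%).
- The same choice with no events: upper limit 30.8% (0/10) against 36.9% (0/8).

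**The case against.** Several points on the other side stand.

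- **The wording is permissive.** The investigator may withdraw the patient; 7.7 does not say that every stopped procedure ends participation. That leaves the matter to discretion and does not close the gap, because no visible text sets out the alternative of stopping the procedure and keeping the patient in follow-up.
- **Relevant text may be hidden.** The Table 1 footnotes, including the one on AEs, and parts of 7.1, 8.1 and 8.2.2 are blacked out. Section 7.7 refers to site termination procedures that are not shown, and section 10.9 to a Safety Management Plan and a DSMB Charter. The finding is limited to the visible text.
- **Withdrawals would be visible.** Disposition by reason and the per-subject listings would show any such case among 10 subjects. They would not show an event that nobody was asked to report.

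Three stronger readings are tempting but unsupported.

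- A reader might infer that these patients have no required safety follow-up at all. Section 12.2 contradicts that for AEs already present.
- A reader might infer that every aborted case dilutes the AE percentages. A patient who received no ablation is outside the FAS wording, so the effect may instead be omission.
- A reader might infer that the SAP contradicts 7.7, since its opening paragraph says "the decision was made to permanently stop study enrollment and follow the 10 previously-enrolled subjects through the end of the study follow-up period". Stopping enrollment is not the site or study termination described in 7.7, and Protocol 7.1 has the study run until patients finish follow-up or withdraw early. The SAP statement shows only that continued follow-up was considered feasible.

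**Conclusion.** The concern holds for new or late-onset AEs and readmissions after withdrawal by the investigator or the sponsor. Applying 7.7, 12.2 and 6.2 as written loses those events, and no planned analysis recovers them. Depending on whether ablation was delivered and whether a date was entered, the affected patient either dilutes the FAS percentages or drops out of them.

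The size is an upper bound on assumed inputs: up to 10% relative per Day 0 withdrawal at N = 10, and 2.5% at N = 40. This takes equal risk across patients and none of the risk falling before withdrawal (f = 0). The documents do not say whether any patient was withdrawn during ablation, so no bias in the actual results can be claimed. The change should be made because it is cheap and protects safety data in a small early study.

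**What to change.** 1. In 7.7, define *procedure discontinued* and *withdrawn from study* as separate events.
2. Keep any patient in whom the procedure was begun in AE, SAE and readmission follow-up through Visit 5, unless consent is withdrawn.
3. Extend the all-efforts sentence to investigator- and sponsor-initiated withdrawals, including ablated patients at a terminated site where feasible. Mandatory full follow-up at a closed site is more debatable and is not needed for this point.
4. Align 12.2 and 6.2 with these definitions.
5. Reconcile the FAS wording in Protocol 10.7 and SAP 9.9 with the programming note under SAP Table 1. State where a patient with the procedure begun but no ablation delivered is counted.
6. For the 10 subjects already enrolled, report each subject's follow-up time and any withdrawal during the procedure.

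The cost is protocol and SAP wording, plus follow-up contacts for a few patients. No decision to stop a procedure changes; only what is collected afterwards does.

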8.0 STUDY PROCEDURES

8.1 Procedure Description(s)

Adult patients with medically inoperable primarily soft tissue lesions of the lung will have a transbronchial microwave ablation

[REDACTED]

[REDACTED]

[REDACTED]

[REDACTED]

[REDACTED]

[REDACTED]

[REDACTED]

[REDACTED]

[REDACTED]

[figure not shown]
[figure not shown]
[figure not shown]
[REDACTED]

Total Radiation Exposure

The total radiation exposure for each patient will be dependent on the number of CTs per patient and the type of CTs, as well as many other factors, such as the manufacturer of the scanning equipment. Conventional CT has an average radiation range 0.1 mSv to 15 uSv,⁶ while the average radiation range for cone beam CT is considerably higher: 19 uSv to 1073 uSv.⁷ The total radiation exposure to the patient during the ablation procedure will be captured.

8.1.1 System Overview(s)

[REDACTED]

[REDACTED]

[REDACTED]

8.1.2 Identity of Study Products

For this study, medical devices will be used in accordance with manufacturer design specifications, product instructions, and guidelines.

TEST PRODUCT: NEUWAVE FLEX MICROWAVE ABLATION SYSTEM AND ACCESSORIES

Product Code	Description
NWF1US1N	NEUWAVE Flex Microwave Ablation System, 120 Vac DR-000770
[REDACTED]	[REDACTED]
[REDACTED]	[REDACTED]
[REDACTED]	[REDACTED]
[REDACTED]	[REDACTED]

8.1.3 Investigational/Study Product Accountability

The NEUWAVE Flex Microwave Ablation System and the microwave ablation probes [REDACTED] must be stored in conditions according to product labeling and IFU. It is the responsibility of the Principal Investigator to ensure that devices are stored correctly at the site.

The Principal Investigator or responsible person designated by the Principal Investigator must account for all study devices throughout and, at the end of, the clinical study. During the course of the study, the study’s ablation probes must be stored in a locked or secure access location. An inventory record must be maintained of all devices received, used or returned during the clinical trial. The Principal Investigator must allow the Study Monitor access to the secured facility where the study devices are stored to check inventory.

The Sponsor will supply the NEUWAVE Flex Microwave Ablation System and the microwave ablation probes to the study sites. Upon receipt, the Investigator will do the following:

- Conduct an inventory.

- Upon confirmation that all materials arrived intact, complete the Packing List for Clinical Supplies included with the shipment. The Sponsor should be contacted immediately if any materials are damaged or missing from the shipment.
- Sign and date the packing list, and promptly return it to the Sponsor.
- Retain a copy of the signed and dated Packing List for Clinical Supplies for the Investigator's records.

The study device inventory must be available for periodic inspection/verification.

8.2 Visits

Table 1: Schedule of Assessments may be found at the end of Section 1.0 Synopsis.

8.2.1 Visit 1 – Screening

The screening assessments for this visit may occur over several dates within 30 days prior to Visit 2.

Patients will be selected for microwave ablation based on the pre-procedure investigations and the Investigator's interpretation of the clinical picture. Eligible patients will be provided with the study information, including the ICF.

The following screening assessments will occur prior to the study procedure:

- Patients must be given ample time to review and sign the ICF.
- Collect demographic information (age at time of Visit 1, sex, race, ethnicity).
- Review and collect medical and surgical history, including date of diagnosis of soft tissue lesion under study, radiation history, and smoking status.
- Collect height and body weight for BMI
- Evaluate ECOG performance status.
- Record the American Society of Anesthesiologists (ASA) score, which is a global score that assesses the physical status of patients before surgery.
- Record all prior medications taken within 30 days of Visit 2 and all current medications, including but not limited to chemotherapy, steroids, anti-inflammatories, NSAIDs, hormonal therapy, homeopathic/natural medications, nutritional supplements, and antibiotics.
- Review inclusion/exclusion criteria and determine if the patient is eligible to participate in the study.
- QOL questionnaires European Organization for Research and Treatment of Cancer (EORTC) QLQ-C30 and the lung-specific QLQ-LC13. The questionnaires may be administered over the phone, as needed.
- Numeric Pain Rating Scale.
- CT scan of the lung to determine soft tissue lesion details (e.g., size, lesion type, location, shape).
- [REDACTED] send the scan to the central radiologist for independent review (refer to the Central Radiology Review manual).
- Obtain PFTs, which may include spirometry, diffusion capacity (also called the DLCO [diffusing capacity of the lung for carbon monoxide]), lung volume tests, pulse oximetry, and FeNO tests.
- Laboratory tests. If the following tests (based on the study site's SOC) will be completed within 30 days of Visit 2, then they do not need to be repeated at the

Screening visit:

- CBC (with differentials).
- Coagulation tests (APTT, INR, PT, PTA, PTT).
- Serum pregnancy test, for women of childbearing potential only.
- Any genetic markers relevant to the lesion, if done per SOC.

8.2.2 Visit 2 – Ablation Procedure Through Discharge (Visit 2B)

[REDACTED]

[REDACTED]

On the day of ablation, cone beam CT scans will be done at the timepoints listed in the section below.

Visit 2A: Intraoperative (Ablation)

Data collected before and during the procedure:

- Administer antibiotics prior to the ablation procedure.
[REDACTED]
- Measure and record the size of the lesion to confirm inclusion criteria (lesion must be ≤ 2 cm).
- Prior to ablation, confirm that the patient still meets inclusion and exclusion criteria (tests not needed to be repeated).
- Collect height and body weight for BMI, and evaluate ECOG performance status (prior to ablation).
- Record all concomitant medications, including but not limited to chemotherapy, steroids, anti-inflammatories, NSAIDs, hormonal therapy, homeopathic /natural medications, nutritional supplements, and antibiotics. Do not record components of the anesthesia medications used for the ablation procedure.
- Record all concomitant procedures.
- QOL questionnaires EORTC QLQ-C30 and the lung-specific QLQ-LC13 (prior to ablation). The questionnaires may be administered over the phone, as needed.
- Numeric Pain Rating Scale (prior to ablation).

[REDACTED]

[REDACTED]

[REDACTED]

[REDACTED]

[REDACTED]

[REDACTED]

[REDACTED]

[REDACTED]

[REDACTED]

[REDACTED]

[REDACTED]

[REDACTED]

[REDACTED]

[REDACTED]

[REDACTED]

[REDACTED]

- User Experience Survey answered by the treating physician post-ablation (available as a separate document).
- Evaluate technical success, defined as ablation of the target lesion according to the protocol and covered completely, with an adequate margin, as defined by the performing physician (that is, the ablation zone completely overlaps or encompasses the target lesion plus an ablative margin).

[REDACTED]

- Radiation exposure from the CT scans.
- Record any AEs/SAEs that occur from the start of the ablation.

Visit 2B: Discharge

After the ablation procedure, the patient will be observed for up to 23 hours and afterwards discharged from the study site (except in cases where the Investigator deems it is necessary for the patient to remain hospitalized). During that 23-hour period, the following assessments will occur:

- Record all concomitant medications.
- Record all concomitant procedures.
- QOL questionnaires EORTC QLQ-C30 and the lung-specific QLQ-LC13. The questionnaires may be administered over the phone, as needed.
- Numeric Pain Rating Scale.
- Length of hospital stay, measured from post-ablation to discharge.

- All AEs/SAEs.
- De-identified UB-04 data, if allowed, to be provided to the Sponsor by the site.

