5.2 Secondary Objectives

The secondary objectives are the following:

1. To evaluate safety through the monitoring of device-related and procedure-related adverse events (AEs) and all serious adverse events (SAEs), from start of ablation through 1-year post-ablation.
2. To establish device and procedure effectiveness by following patients for 1-year post-ablation to ensure completeness and durability of treatment effect, based on standard endpoints in microwave ablation, as follows:
 - a. Primary efficacy rate
 - b. Secondary efficacy rate
 - c. Local soft lesion recurrence
 - d. Length of hospital stay (LOS)
 - e. Hospital readmission rate.
3. To calculate length of hospital stay (LOS), measured from post-ablation to discharge.
4. To calculate hospital readmission rate, defined as any readmission to the hospital within 30 days of the first ablation procedure (Visit 2A).

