6.2 Secondary Endpoints

The secondary endpoints include the following:

- Any complications attributable to the procedure, including all device-related, procedure-related, and serious adverse events (SAEs), evaluated from the start of ablation through 30 days \pm 7 days post application of ablation and from the start of ablation through end of follow-up (1-year post-ablation) or early discontinuation.
- Primary efficacy rate, defined as the percentage of target soft tissue lesions successfully eradicated following the ablation procedure, as assessed using CT imaging.
- Secondary efficacy rate, defined as the percentage of soft tissue lesions that have undergone successful repeat ablation following identification of local soft tissue lesion progression, as assessed using CT imaging.
- Target lesion recurrence, defined as reappearance of the lesion at the treated site, as assessed using CT imaging.
- Length of stay, measured from after the ablation procedure until the patient is discharged home.
- Hospital readmission rate, defined as any readmission to the hospital within 30 days.

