10.9 Analyses to be Conducted

Analyses described below will be performed on the pooled set of 40 patients [REDACTED]

Disposition of Study Patients

Patient disposition will be summarized using counts and percentages. The number and percentage of patients completed and discontinued along with the specific reasons for discontinuation will be tabulated by treatment group and in total.

Demographic and Baseline Characteristics

Summary statistics will be provided for patient demographics and pre-operative ablation characteristics.

Primary and Secondary Endpoint Analyses

Device user experience feedback will be collected from the treating physician who will complete the User Experience Survey following each ablation procedure. The questionnaire will focus on procedure workflow and the user's assessment on ease/difficulty of using the device. Summary statistics will be provided for each question.

The number and percentage of patients achieving technical success will be summarized and a 95% confidence interval will be estimated. Technique efficacy, as well as primary and secondary efficacy rates and hospital readmission rates, will be summarized in a similar manner. Local soft tissue lesion recurrence rates will be estimated using the Kaplan-Meier method and 95% confidence intervals will be provided.

The number and percentage of patients experiencing AEs from the start of ablation (Visit 2A) to Visit 3 (the first post-ablation visit) will be summarized by MedDRA preferred term and system organ class. A similar summary will also be provided for device related and procedure related, and all SAEs. Ninety-five percent confidence intervals may be provided for pre-specified adverse events of interest [REDACTED]

[REDACTED]

[REDACTED]

[REDACTED]

[REDACTED]

[REDACTED]

[REDACTED]

[REDACTED]

[REDACTED]

[REDACTED]

[REDACTED]

Similar summaries will also be provided for the entire observation period from the ablation procedure date through 1 year of follow-up.

The EORTC QOL questionnaires and Numeric Pain Rating Scale scores will be summarized with methodology consistent to the recommendations of the specific survey. Additional endpoints will be summarized with descriptive statistics.

Plans for Interim Analysis

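### The start of adverse event collection is worded inconsistently, so same-session complications before ablation may be missed, and subjects accessed but not ablated drop out of the safety tables

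*Protocol*

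**What the plan says.** The narrow anchor, the start of ablation, appears in most places. The safety objective in protocol 5.2 runs "from start of ablation through 1-year post-ablation", and SAP 1.1 repeats it. The safety endpoint in protocol 6.2 reads "Any complications attributable to the procedure, including all device-related, procedure-related, and serious adverse events (SAEs), evaluated from the start of ablation". The synopsis matches both. The instruction that site staff follow at Visit 2A (protocol 8.2.2) is "Record any AEs/SAEs that occur from the start of the ablation".

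A broader anchor appears elsewhere. Protocol 12.2, which sets the reporting duty, requires all AEs "from the start of the ablation procedure (Visit 2A) until the patient completes Visit 5". Protocol 10.9 writes "The number and percentage of patients experiencing AEs from the start of ablation (Visit 2A) to Visit 3", which attaches the visit label to the narrow phrase. The full-period summary starts at the date of the ablation procedure in 10.9 and at Visit 2A in the synopsis.

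SAP 9.6 sets no onset limit for the overall AE tables. It counts its 30-day summaries after the initial ablation procedure.

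On subjects who are not ablated:
- Protocol 7.7 lists reasons for withdrawal during the ablation procedure. They are failure to find and target the lesion, and "Inability of patient to tolerate the anesthesia".
- Protocol 7.6 makes a consented patient whose ablation procedure is not initiated a screen failure. It names only the demographics and reason-for-failure pages.
- Protocol 10.7 and SAP sections 6 and 9.9 restrict the summaries to subjects who receive ablation through the probe.

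**The concern.** The scope of the endpoint and its clock do not match. The endpoint covers complications of the procedure as a whole, while the clock in the endpoint and in the site instruction starts at ablation. No visible text says whether that means induction of anaesthesia, scope insertion, probe placement or energy delivery.

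The earlier part of the session carries its own risk. Table 1 places CP-EBUS at Visit 2A, and a positive node is an exclusion criterion (7.4, item 15), so it must come before ablation. Section 8.2.2 also uses the phrase *prior to ablation* for other tasks at the same visit. A coordinator could therefore take the start of the ablation to be a later moment and leave an earlier bleed or pneumothorax off the form.

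Protocol 4.0 argues that endobronchial access limits complications such as pneumothorax and hemoptysis. SAP section 7 names pneumothorax and hemorrhage as events of interest and intends a comparison with published rates. Access-phase events bear directly on that comparison, and any omission can only lower the observed rate.

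**Working it through.** The plan states no figure on this point, so there is nothing to reproduce. The check sets the wordings side by side, follows the two kinds of subject through the plan, and adds one illustration.

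**1. Start points as written**

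| Place | Start of AE window |
|---|---|
| Synopsis objectives and endpoints; protocol 5.2, 6.2; SAP 1.1 | start of ablation |
| Protocol 8.2.2 (site instruction) | start of the ablation |
| Synopsis statistics and protocol 10.9, summary to Visit 3 | start of ablation, labelled Visit 2A |
| Synopsis, full period | Visit 2A |
| Protocol 10.9, full period | date of the ablation procedure |
| Protocol 12.2 | start of the ablation procedure, labelled Visit 2A |
| SAP 9.6, overall tables | none stated |
| SAP 9.6, 30-day summaries | after the initial ablation procedure |
| Table 1 | marked at Visit 2A; footnote 18 redacted |

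Table 1 has no prior-to-ablation asterisk on the AE row, but that settles nothing. CP-EBUS and the quality-of-life forms also lack it at Visit 2A. The quality-of-life forms are stated in 8.2.2 to come before ablation, and CP-EBUS must do so.

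**2. A subject who is ablated after an access complication**
- Narrow reading (6.2, 8.2.2): onset precedes the window and the event may not be entered.
- Broad reading (12.2 with 7.7): anaesthesia and targeting belong to the ablation procedure, so the event is reportable. Once entered it reaches the overall tables, because SAP 9.6 has no onset cut-off. Its place in the 30-day summaries is uncertain, because they count from after the procedure.

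**3. A subject accessed but not ablated**
- If the procedure counts as initiated (7.7), 12.2 requires AE reporting until withdrawal. The event can appear in SAP Listing 29, which covers all subjects.
- If it counts as not initiated (7.6), the subject is a screen failure. No AE page is named, so the event may not reach the database.
- Either way the subject did not receive ablation and is outside the Full Analysis Set. The programming note to SAP Table 1 identifies the set by a recorded ablation date. SAP Tables 14–21 all use that set, so the event enters no summary.

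**4. Illustration, ablated subjects only**

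Input: n = 10 ablated (SAP section 7). Exact (Clopper-Pearson) 95% limits:
- 0/10: upper limit = 1 − 0.025^(1/10) = 30.8%; interval 0–30.8%.
- 1/10: lower limit = 1 − 0.975^(1/10) = 0.3%; upper limit = 97.5th percentile of Beta(2, 9) = 44.5%.

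The documents give no rate p of pre-ablation events per subject. The chance of at least one event among 10 is 1 − (1 − p)^10, over an assumed range:

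| Assumed p | At least one in 10 |
|---|---|
| 1% | 9.6% |
| 2% | 18.3% |
| 5% | 40.1% |
| 10% | 65.1% |

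These are chances that such an event occurs, not that it goes unrecorded.

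**The case against.** The strongest reply is that the reporting duty lies in 12.2, and 12.2 is broad. Section 7.7 itself places anaesthesia and targeting inside the ablation procedure. Section 12.1 requires all AEs to be recorded whether or not they are attributed to device or procedure. Section 10.9 and the synopsis tie the narrow phrase to Visit 2A, and the full-period summaries start at the visit or the calendar date. The overall tables in SAP 9.6 have no onset cut-off. The procedure steps and Table 1 footnote 18 are redacted and may define the start. Safety is a secondary objective in a descriptive study without hypotheses.

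Most of this stands. It rules out the stronger inference a reader might draw, that the plan definitely excludes access-phase events and so under-counts in the device's favour. The documents do not show that, and no omitted event is known.

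The inconsistency remains. The endpoint and the visit instruction carry the narrow phrase, and nothing visible says that 12.2 overrides them. Nor does the reply close the gap for subjects who were not ablated: even under the broad reading, their events reach a listing and no table.

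Two limits on the illustration also stand. The change from 1/10 to 0/10 would follow from any missed event in any 10-subject study. It also cannot be applied to aborted cases, because those subjects are not among the 10.

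**Conclusion.** The point holds as an inconsistent and visibly undefined start of AE collection that may, on a literal reading, lose same-session complications arising before ablation. It does not hold as a demonstrated under-count.

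A second, separate gap is firmer. A subject in whom access was started but no ablation given contributes to no safety table and, if handled as a screen failure, possibly not to the database. This assumes that no ablation date was entered for such a subject. The documents do not say how many there were.

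The size is unknown. For the 10 ablated subjects, one missed event changes 1/10 (0.3–44.5%) to 0/10 (0–30.8%). The SAP plans no confidence intervals for AEs, so these only show scale. The conclusion rests on the visible text; an explicit definition in the redacted footnote would remove the first gap but, unless it also dealt with analysis sets, not the second. The sponsor should correct this, but it does not undermine the study.

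**What to change.** 1. Use one start point for AE collection and analysis in the synopsis, protocol 5.2, 6.2, 8.2.2, 10.9 and 12.2, and in SAP 1.1 and 9.6. It should cover the whole Visit 2A session: start of anaesthesia or insertion of the bronchoscope, whichever is first, whether or not ablation follows.
2. Enrolment has stopped, so new protocol wording cannot change what was collected at Visit 2A. Check the Visit 2A source records of the 10 ablated subjects and of any aborted attempts for unentered events.
3. State in SAP 9.6 that AEs with onset at Visit 2A from that point count in both the overall and the 30-day summaries.
4. Report AEs in subjects accessed but not ablated separately, with their own denominator. The Full Analysis Set need not change.

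The cost is wording changes and a small source check. AE counts may rise.
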